6.0 Number of Subjects

We will recruit up to 10 participants for individual interviews and 106 for the RCT, the first 5 of the RCT will be for usability testing.

7.0 Setting

Study participants will be recruited from primary care/family medicine practices affiliated with MUSC's Primary Care Integrated Center of Clinical Excellence (ICCE). Participants may also be recruited remotely via advertisements (e.g., online ads).

8.0 Recruitment Methods

Recruitment will occur proactively and remotely leveraging data available within the EHR. As part of routine clinical care, adolescents are screened at each visit for nicotine/tobacco use, including e-cigarette use, and for depressive symptoms via the Patient Health Questionnaire-2 (PHQ-2). To recruit our targeted population, we will utilize cold contact methods by submitting a Research Data Request to obtain a EHR recruitment report created for all patients treated within the Primary Care ICCE during the past 12 months who: 1) are age 16-20, 2) vape, and 3) had depressive symptoms during their last visit. Depressive symptoms will be defined as *either*: 1) a score of ≥ 3 on their last PHQ-2 (the optimal cut-point to identify those symptomatic), 2) depression on their problem list, *or* 3) a depression-related billing code. The study team will not cold-contact any patients who have chosen to opt-out of receiving contact about research or who have met the maximum number of contact attempts at the time of recruitment.

Identified patients will be sent an electronic communication (e-mail or message via the EHR patient portal, based on patient preferences) from a member of the study team inviting them to participate in a study. This electronic communication will include a link to complete study screening via REDCap. Within South Carolina, the legal age to consent to medical treatment is 16. At age 16, all MUSC patients can receive their own patient portal account and parents/guardians can be appointed as proxies. If participants do not respond to this invitation within 72-hours, we will contact them via phone, e-mail, and/or text-message (based on preferences within the EHR) to ensure they received the message. If interested, participants will complete an eligibility screening via MyChart/REDCap. This eligibility screening will assess: age, sex, e-mail access, English fluency, smartphone ownership, nicotine vaping status, willingness to use a mobile app for nicotine vaping cessation, and depressive symptoms via the PHQ-8. This eligibility screening will be used solely for screening purposes, not for research purposes. Within our informed consent documents, if a participant provides informed consent to participate in the study, they will agree that their screening information can be used for research purposes. After completing determination of eligibility, a member of the research team will complete remote electronic informed consent with the participant (see details below).

Recruitment may also occur in the following ways:

- 1) In Clinic: Participants may be recruited in clinic after being identified as a nicotine vaper by research personnel listed on this application.
- 2) Via advertisements (e.g., flyers) and online postings such as Craigslist.
- 3) Snowball recruitment: Enrolled participants can refer others to the study. If they refer someone that enrolls, they will receive additional compensation.
- 4) Recruiting parents with children who vape directly using IRB approved advertisements on online platforms.

9.0 Consent Process

Signed informed consent will be obtained from study participants. The consent process will take place via one of the following modalities: 1) Remote or in person electronic consent (e-consent) via REDCap (if remote, e-consent will be facilitated with a discussion over the phone or via video), 2) Remote consent via doxy.me facilitated with either a discussion over the phone or video connection via doxy.me, 3) Mailed

(paper) consent facilitated with a discussion over the phone, or 4) in person consent (e.g., in clinic, in the investigator's lab space).

All participants will be provided with a hard copy and/or an electronic copy of the consent form. Participants will be informed that participation in this research is strictly voluntary. Informed consent will include a detailed description of the purpose and the procedure of the study emphasizing our policy regarding privacy and confidentiality and an opportunity for the individual to ask any questions or voice concerns. Signatures on the consent form may be obtained with paper and pen OR electronically via REDCap/doxy.me. Participants who do not have access to the required technology to complete consent remotely via REDCap or doxy.me will be given the option to complete consent via mail facilitated with a discussion over the phone.

Parents/guardians of participants under 18 years old will be required to attend the informed consent/assent procedure. Participants 18 years and older will be able to provide their own informed consent. Particular caution will be exercised in obtaining informed adolescent assent separately and independently from parental consent to limit potential for coercion. To this end, an initial step in participant recruitment involves obtaining parental/legal guardian permission for participation by the adolescent. Once parental consent is secured, youth will be asked separately and independently for informed consent (i.e., parental consent will not be used to persuade teens to participate). This approach is considered very effective in minimizing coercion to participate. In the case of adolescents in South Carolina Department of Social Services custody, state guidelines regarding consent for clinical research participation will be followed.

10.0 Study Design / Methods

Aim 1: Develop and Refine VapeX.

VapeX Development Testing

VapeX development will take place in three steps: 1) semi-structured individual interviews with end-users (n=10) and 2) software development. Individual interviews will follow standard procedures⁵¹. Individual interviews (1hr each, \$40 compensation in electronic gift card codes (e.g., Amazon) emailed to participants) will be divided into four parts: 1) discussion of apps for positive health behavior change and participants' experiences with such apps, 2) narrowed focus on mobile apps for quitting vaping and managing low mood, 3) even narrower focus on an initial version of the VapeX app, which will be previewed for the participant during the interview, and 4) discussion of features that participants would like included in VapeX that are not currently included. This discussion will begin with facilitators presenting participants with a list of features that have been included in other mobile app interventions for adolescent substance use treatment (**Table 1**)^{52,53}. Individual interviews may occur either remotely using an MUSC-approved HIPAA compliant video conferencing platform (e.g., Microsoft Teams) or in person, depending on the status of the COVID-19 pandemic.

Features identified via individual interviews will form the basis of VapeX development. VapeX will be developed for iOS and Android, will be HIPAA-compliant, and will retain all key elements of Brief BA and standard cessation treatment in Goal2Quit, though these features will be modified based on individual interviews. Brief BA components include: 1) Psychoeducation highlighting the connection between mood and vaping, 2) Identification of values and activities across life areas including relationships, responsibilities, recreation, education/career, health, and being vape-free, 3) Activity planning, and 4) Tracking mood and vaping. Standard cessation components include: 1) Reinforcement and support for

Table 1: App Features to Consider for VapeX

Domain	Specific Potential Features
Gamification	Rewards earned for continued app use or decreased vaping; Competitions within the app
Social Interaction	In-app communication with peers; Ability to help others quit vaping/provide peer support
Family Involvement	Resources for discussing depressed mood and/or substance use with parents
Dual Use	Psychoeducation about dual use and strategies to quit smoking while quitting vaping

quitting, 2) Interactive questions to identify past quit attempts and contributors to relapse, 3) Setting a quit date, suggested to be no later than two weeks after treatment initiation, and 4) Identification of triggers and development of coping strategies. As in prior projects, to develop VapeX, we will follow an agile software development approach⁵⁴. Key phases of development will include whiteboard design, wireframing of user stories, graphic design, programming, and deployment. Development will be led by MountainPass Technology LLC, with iterative testing completed by the PI and co-Is.

HIPAA Compliance

Regarding user privacy while using VapeX, users will create a username and password in order to login to their account without storing their true identity. In VapeX, we will store a one-way hashed version of the patient's email address to support password reset and unique identification, but that identification will not be traceable back to the user's true identity. We will not store any personally identifiable information (e.g., first name, last name, email address, phone number) of users in our app database. VapeX will be HIPAA compliant. We will use a HIPAA-compliant server protected by industry-standard safeguards to prevent unauthorized access. Since we are not associating patient health information with personally identifiable information there will not be a risk of unauthorized release of patient medical data in the event of a security breach. User personal information will be contained behind secured networks and will only be accessible by the investigators, who will have special access rights to such systems. In addition, all sensitive information users supply will be encrypted via Secure Socket Layer (SSL) technology. We will not sell, trade, or otherwise transfer personally identifiable information to outside parties. Our privacy policy will be available within the app for users to view at any time. This plan is consistent with that used by our partnering app development company, MountainPass Technology LLC, in several other previous products with similar protection requirements. [name] from MountainPass Technology has expertise in HIPAA-compliant software development and will oversee all aspects of HIPAA compliance within this project.

Aim 2: Pilot Feasibility RCT (N=106) of VapeX vs. TAU.

Procedures

After completing determination of eligibility and consent, usability testing will commence. Recruitment will continue until we reach data saturation (planned n=5)⁵⁶. The first 5 participants enrolled will be assigned to the VapeX group to assess to capture any app refinements necessary at the start of the trial. All other procedures while remain the same across participants. The remaining participants (n=98) will be randomized via REDCap 1:1 to VapeX or TAU. Participants will be randomized via a mixed block design stratified by age, baseline depressive symptoms, and concurrent depression treatment. All participants will complete baseline assessments remotely and if randomized to VapeX, study staff will remotely provide participants with app download codes and will ensure successful downloads. Study staff will then give participants brief overviews regarding app utilization and will provide the participants 10 minutes to use the app and ask questions.

Assessments

Participants will be text messaged or emailed a REDCap link to complete follow-up assessments **weekly for 4 weeks**. Assessments are estimated at 20 minutes each. Participants will be compensated in electronic gift card codes (e.g., Amazon) emailed to participants in the amount of \$20 for completion of each assessment with a \$50 bonus if all are completed. If a participant does not meet final eligibility at baseline, they will be compensated \$20 for the visit but will not be enrolled. Enrolled participants may also refer others to this study. If they refer someone that is eligible and enrolls they will receive an additional \$40 (Total possible compensation = \$190). If fraud is detected within the surveys, the Principal Investigator may decide to withdraw a participant from the study. Fraud may include 1) a research assessment being completed in an unusually short period of time, 2) straightlining (i.e., responding with the same answer to

all items on a survey), 3) inaccurate responses to a validity check question. If fraud is suspected, the study team may request additional verification of identity such as a photo ID prior to trial enrollment.

Vaping. Nicotine vaping and quit outcomes will be assessed at each follow-up using a Timeline Followback for the last 6-months at baseline and since prior follow-up for each subsequent assessment⁵⁹. Frequency of vaping will be assessed in multiple ways including number of vaping episodes per day and number of days per week vaping. Use of other tobacco products and frequency of use will also be assessed. Cessation outcomes include: 1) number of quit attempts since last assessment, 2) duration of each quit attempt, 3) point-prevalence abstinence, and 4) continuous abstinence. E-cigarette dependence will be assessed at baseline via the 10-item Penn State Electronic Cigarette Dependence Index (ECDI)^{60,61}. Participants will report motivation to quit and confidence in quitting using a modified Contemplation Ladder⁶². Depression. The clinic-administered PHQ-2⁶³ will be used for preliminary her screening and the PHQ-8 will be completed during initial screening. As the PHQ-8 does not assess suicidality, the full PHQ-9⁴⁷ will be administered at final screening. Across all timepoints depressive symptoms will also be assessed via the Beck Depression Inventory-II (BDI-II)^{64,65}. The BDI-II is a validated assessment of depressive symptoms among adolescents⁶⁵ and is our primary depression outcome. Self-report EHR data will be used to categorize concurrent depression treatment (therapy, medications) at baseline and across the trial. Treatment Utilization. VapeX utilization will be tracked via analytics data. Specifically, we will examine 1) number of app sessions, 2) average time per session, and 3) total time using the app. Additionally, we will assess engagement with each individual component of the app. Components will be finalized based on feedback from individual interviews but are likely to include identification of activities, scheduling of activities, mood tracking, monitoring frequency of vaping, and standard vaping cessation treatment content (e.g., setting a quit date, education about the benefits of quitting vaping). Participants will be asked to use the app at least once per day for at least 5-10 minutes at a time. Analytics will be examined within each week and across the entire trial duration. VapeX Feasibility and Acceptability. VapeX participants will self-report feasibility and acceptability at all follow-ups. As in our prior trials, participants will report: 1) ease of app use, 2) continued desire to use the app, 3) perceived benefits of using the app, and 4) suggested improvements.

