
11.0 Data Analysis and Data Management

Data Analytic Plan for Aim 1 Qualitative Data

Qualitative data from interviews, quantitative data from questionnaires, and video and audio recordings will be incorporated for mixed methods data analysis⁶⁶. This approach was chosen because, while quantitative data can identify usability errors and areas of dissatisfaction, qualitative data provides guidance on the root of errors and methods for optimization. Qualitative data will be analyzed using NVivo software⁶⁷ and a deductive/inductive template analysis approach^{68,69} using iterative codes to identify core concepts⁷⁰. From these core concepts, we will determine the needs, concerns, and impressions of our prototypes. Two coders will independently review and code data using an iterative, team-based process with discrepancies resolved by the study team. Qualitative themes will be supplemented by patterns identified in quantitative results. After completing qualitative and quantitative data analysis independently, data from each source will be synthesized using graphical matrix configurations for data triangulation⁷¹. This analytic approach was selected due to the expectation that participants will raise unanticipated needs. Mean ratings of VapeX components from the After-Scenario Questionnaires (ASQs) will be calculated and components with lowest satisfaction will be flagged for refinement. Video and audio recordings be coded for navigation errors (difficulty locating a function), content errors (difficulty due to information labeling), and usage errors (improper tool use). Problems will be grouped according to severity (critical/serious/minor).

Sample Size Estimation

As a pilot, our goal is to determine VapeX feasibility/acceptability and estimate effect sizes for a larger Phase II project. We can obtain more robust estimates in the VapeX group via 1:1 randomization with the first 5 being assigned to the VapeX group for usability testing. Toward these ends, we will randomize **49 to VapeX and 49 to TAU**. To account for 20% attrition, we will enroll a maximum of 108 participants.

Data Analytic Plan for Aim 2

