Feasibility and Acceptability. Within the VapeX group, retention will be defined as the proportion of participants who use the app at least once within each week following enrollment. Retention point estimates and 95% CIs will be calculated, and a one-sided, one-sample proportion test will be used to determine whether retention is at least 70% (or higher) within each group. Other metrics of feasibility/acceptability (ease of use, continued desire to use, etc.) will be summarized within group via summary statistics and 95% CIs, as appropriate.

Vaping Behavior and Vaping Cessation Outcomes. Descriptive statistics will be calculated and compared for overall group differences via Fisher's exact tests, chi-square tests, or nonparametric equivalents, as necessary, for baseline variables. Pairwise differences will be explored for categorical variables that show a significant overall group difference to see where differences may exist. Significant baseline demographic differences between groups will be included as covariates in vaping and depression outcomes analyses. Descriptive statistics (e.g., means, frequencies, percentages) will be calculated for the primary vaping-related outcomes including frequency of vaping and other tobacco product use (number of e-cigarette use episodes per day, number of days using an e-cigarette per week, number of days using other tobacco products including cigarettes) and vaping cessation outcomes (number and duration of e-cigarette quit attempts, 7-day point prevalence abstinence at Week 4) overall and by treatment group. To examine group differences adjusted for relevant covariates based on baseline differences between groups, generalized linear mixed models with logit links for binary outcomes will be used, including a random component for participant and/or clinic. These mixed models will account for any clustering effects within participant and clinics.

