Depression. Similar generalized linear mixed models will be used to examine group differences (VapeX vs. TAU) in depression (BDI-II) over time along with an interaction between group and time adjusting for baseline differences and baseline depression. All models will include a random component to account for any clustering effects from the clinic from which the participant was recruited along with a random effect for repeated measures within an individual. Sex will be examined for inclusion as a covariate in all models. These generalized linear models allow for examination of overall main effects of group, time, and the interaction between group and time, while also accounting for repeated measures within participants and clustering with clinics^{72,73}.

Missing Data. All randomized participants will be included in primary analyses, and imputation methods will be used to accommodate missing data if missing data is >10%. Sensitivity analyses will be done using only those with complete data, with results compared to primary analyses. Attrition will be assessed to determine whether there is differential dropout by group.

Adverse Events (AEs). AEs will be defined as a clinically significant (i.e., 10-point⁶⁴) increase in depression on the BDI-II from baseline or any incidence of suicidality (response of "I would like to kill myself" or "I would kill myself if I had the chance" on the BDI-II suicidality item). We will determine the incidence of AEs and associated 95% CIs. A chi-square test will determine if the rate of AEs is greater than 5% in any group.

Data Management

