This R41 application consists of a 2-Aim proposal. In Aim 1, targeted end-users, defined as adolescent (ages 16-20) regular nicotine vapers (vaped on ≥ 20 days out of the last 30⁴⁶) with elevated depressive symptoms (score of ≥ 10 on the PHQ-9⁴⁷) who have been seen at least once in the last year by a PCP, will be recruited for individual interviews (n=10) that will inform the development of VapeX. In Aim 2, we will conduct a two-arm pilot feasibility randomized controlled trial (N=106; 1:1 randomization) with the first 5 participants recruited for usability testing and randomized to receive the VapeX app, to examine the feasibility and acceptability of VapeX as well as treatment efficacy for depression and nicotine vaping cessation relative to TAU.

Trial Management

The study will be managed from the Addiction Sciences Division within the Department of Psychiatry and Behavioral Sciences at the Medical University of South Carolina (MUSC). Recruitment, data collection, data management, and treatment provision will be coordinated and centrally managed at our research lab at MUSC and will be implemented within local Family Medicine/Primary Care clinics that are part of MUSC's Primary Care ICCE.

Data Management and Analysis

Participants will enter data in REDCap, a secure, web-based application designed exclusively to support data capture for research studies. REDCap provides: 1) an intuitive interface for data entry (with data validation); 2) audit trails for tracking data manipulation and export procedures; 3) automated export procedures for seamless data downloads to common statistical packages (SPSS, SAS, Stata, R); 4) procedures for importing data from external sources; and 5) advanced features, such as branching logic and calculated fields. These procedures are effective in minimizing data entry errors (e.g., missing or errant

data). All data from VapeX will be stored on a HIPAA-compliant server. Data analytic plans are outlined above.

Quality Assurance

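### The first five VapeX participants are assigned in two sections but called randomised in a third, and the enrolment totals of 106 and 108 do not follow from 5 + 98

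*Combined protocol and SAP*

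**What the plan says.** **Allocation.** Section 10.0 (Aim 2, Procedures) says "The first 5 participants enrolled will be assigned to the VapeX group", and then "The remaining participants (n=98) will be randomized via REDCap 1:1 to VapeX or TAU". The number five is a plan; recruitment to usability testing runs until saturation. Section 11.0 (Sample Size Estimation) also treats the five as assigned ("with the first 5 being assigned to the VapeX group for usability testing") and randomises 49 to each arm. Section 12.0 (Summary of the Protocol) instead describes a 1:1 trial of 106 "with the first 5 participants recruited for usability testing and randomized to receive the VapeX app". Section 6.0 places the five within the 106 RCT participants.

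**Analysis sets.** Section 11.0 (Missing Data) says "All randomized participants will be included in primary analyses". For feasibility, Section 11.0 says "Within the VapeX group, retention will be defined as the proportion of participants who use the app at least once within each week", followed by "a one-sided, one-sample proportion test will be used to determine whether retention is at least 70% (or higher) within each group". It gives no number for the VapeX group.

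**Totals.** 106 appears in Section 1.0, Section 6.0, the Aim 2 heading of Section 10.0, and Section 12.0. Section 11.0 (Sample Size Estimation) caps enrolment at 108 and attributes that figure to 20% attrition.

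**The concern.** Membership of the primary analysis set depends on whether a person was randomised, and the plan describes the same five people both ways. If the Section 12.0 wording were followed, one arm only would gain participants who were allocated by order of enrolment, have no concurrent TAU controls, and may have used the app before the refinements their own testing was meant to prompt. The pilot's stated goals are to determine feasibility and acceptability and to estimate effect sizes for a larger project, so both outputs depend on who is counted.

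A reader would normally use the headcounts to resolve such a conflict. Here they cannot, because the randomised number, the usability number and the two totals do not fit together. The retention test raises a smaller version of the same question: its denominator could be 49 or 54.

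**Working it through.** **1. Headcount.** Inputs: 5 assigned (Sections 10.0 and 11.0); 49 + 49 randomised (Section 11.0).
- 49 + 49 = 98, which reproduces the 98 in Section 10.0.
- 5 + 98 = 103. The documents give 106 in four places and 108 in one.

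**2. The 108 cap.** Inputs: 98 and 20% attrition. If 98 is the number of completers wanted:
- 98 / (1 − 0.20) = 122.5, so 123.
- 98 × 1.20 = 117.6, so 118.
- Neither gives 108. The attrition that 108 allows is 1 − 98/108 = 9.3%. If the five sit inside the cap it is 1 − 98/(108 − 5) = 4.9%.

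If 98 is instead the number randomised, as Sections 10.0 and 11.0 literally say, attrition comes out of the 98 and does not explain 108 at all.

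**3. Efficacy set.**
- Sections 10.0 and 11.0: the five are assigned, so everyone randomised means 49 vs 49 (98).
- Section 12.0: the five are randomised, so it means 54 vs 49 (103), and 5/54 = 9.3% of the VapeX arm was not in fact randomised.
- Precision, in units of the outcome SD: √(1/54 + 1/49) = 0.197 with the five and √(2/49) = 0.202 without. The ratio is 1.024, about 2%.

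**4. Retention test.** Assumptions: exact binomial test against 70%, one test on the VapeX group, one-sided alpha 0.05 (the plan states neither the alpha nor the exact form).

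| | n = 49 | n = 54 |
|---|---|---|
| Smallest passing count | 40 (81.6%) | 44 (81.5%) |
| Exact p at that count | 0.048 | 0.041 |
| Power at assumed true 85% | 0.809 | 0.822 |
| Smallest passing count at one-sided 0.025 | 41 (83.7%) | 45 (83.3%) |

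Near the threshold the five can change the result in either direction:
- 39/49 fails (p = 0.092); with all five retained, 44/54 passes (p = 0.041).
- 40/49 passes (p = 0.048); with three of the five retained, 43/54 fails (p = 0.078).

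If all 54 share one true retention rate, the two denominators disagree in about 2% of trials at a true 70%, 9% at 80% and 6% at 85%.

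**The case against.** **The efficacy set is already nearly settled.** The procedures and sample-size sections both say the five are assigned, and the primary analyses take those randomised. The contrary reading rests mainly on one word in a monitoring summary, applied to people who all receive the same arm, and that summary refers back to the analytic plan. This objection stands to a large extent: exclusion is the more natural reading. What remains is that no section says the five are excluded, and Section 6.0 counts them within the RCT.

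**Evidence that the sponsor means to pool the five is thin.** A reader might infer pooling from "We can obtain more robust estimates in the VapeX group via 1:1 randomization", but that phrase credits the 1:1 randomisation at least as much as the five, and it says nothing about the analysis. A reader might also take Section 1.0 as placing the five inside a trial of 106 randomised 1:1. It does not: it mentions usability testing separately, as a subsequent step.

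**Retention is a single-arm proportion.** Lack of randomisation cannot bias a comparison that is not being made. The five are assigned to the VapeX group and retention is defined within that group, so the literal wording leans to 54. This stands. A possible difference in app version is a reason to look at the five separately, but making 49 the primary denominator would be a preference. The practical effect is small, and the flips above are boundary cases.

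**The totals are a separate defect.** They do not determine who is analysed. That is fair, but they are wrong as they stand, and the same edits that give the five one status will correct them.

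**Conclusion.** The inconsistency is real and should be fixed. The documents give the first five two different statuses. The likely efficacy set is 49 vs 49, but 54 vs 49 can be read from Section 12.0, with 9.3% of the VapeX arm then non-randomised. The size of any resulting bias cannot be derived from the documents.

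The totals are wrong on their face: 103 is neither 106 nor 108, and 108 allows 9.3% or 4.9% attrition rather than 20% if 98 is a completer target. If 98 is the number randomised, attrition does not explain 108.

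The retention denominator is unstated, but the required rate hardly changes (81.6% vs 81.5%) and power is 0.81 vs 0.82, assuming true retention of 85% and one-sided alpha 0.05. All figures that use 5 or 54 assume that usability testing stops at the planned five.

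Two stronger inferences are not supported. The documents do not show that the arm comparison will be contaminated by non-randomised participants. Nor do they show that more people must be enrolled, because they do not settle whether 98 means randomised or completing.

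**What to change.** 1. Section 12.0 (Summary of the Protocol): describe the usability participants as assigned to VapeX, not randomised.
2. Section 11.0 (Missing Data): state that VapeX vs TAU comparisons use only participants randomised 1:1 (planned 49:49).
3. Section 1.0, Section 6.0, the Aim 2 heading of Section 10.0, Section 11.0 (Sample Size Estimation) and Section 12.0: give the usability number (five, or as many as saturation requires) and the randomised number (98) separately. Say whether 98 is randomised or completing, and restate 106, 108 and the 20% attrition statement so that they agree.
4. Section 11.0 (Feasibility and Acceptability): fix in advance whether the 70% test uses 49 or 54, and report the other as a sensitivity result. Either choice resolves the point; the present wording leans to 54.

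**Cost.** These are edits to the text, best made before outcomes by arm are seen. If 49:49 was always intended, restricting the comparisons costs nothing. If pooling was intended for efficacy, the standard error of the group difference rises by about 2%. Naming either retention denominator changes power by about one percentage point under the assumptions above.
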